Note: when patients during the study leave the ICU or intermediate care unit, but are still in the hospital, attempts should be made to continue with the 6-hour urine collection. If the patient is discharged from the ICU or intermediate care unit, the Foley catheter might be removed. In this case, a patient might urinate spontaneously and all efforts should be undertaken to start collecting urine produced from this time point onward. Approximately 6 hours later (exact duration needs to be recorded) the patient might urinate again and this

urine will be used for analysis, a blood sample will be drawn at this time too. The urine volume produced over the last approximately 6 hours will be entered in the eCRF. When patients are discharged from the hospital, 6-hour urine collection at home is not considered feasible or reliable and, thus, will not be performed.

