- l. Creatinine and BUN will be measured by a central laboratory. At Days 60 and 90, only serum creatinine will be measured. When patients have a Foley catheter, serum creatinine samples should be collected prior to and immediately after each urine collection for at least up to Day 7. If the patient is discharged from the ICU or intermediate care unit, the Foley catheter might be removed. In this case, a patient might urinate spontaneously and all efforts should be undertaken to start collecting urine produced from this time point onward. Approximately 6 hours later (exact duration needs to be recorded) the patient might urinate again and this urine will be used for analysis, and a blood sample will be drawn at this time too. The urine volume produced over approximately 6 hours will be entered in the eCRF.
  - m. Urine creatinine and urea will be measured by a central laboratory. The central laboratory will calculate blood urea nitrogen (BUN) clearance at all visits from Day 1 to Day 7, inclusive, and on subsequent visit days if reliable urine collection is possible. Urine will be collected within a  $6 \pm 1$  hour period at all visits from Day 1 to Day 28, only if reliable urine collection is possible (i.e., patient remains in the ICU or intermediate care unit or hospital).
  - n. These assessments will be performed before treatment if possible. Treatment should not be delayed because of these assessments.
  - o. Urine volume collection in a  $6 \pm 1$  hour collection period, only if reliable urine collection is possible (i.e., patient remains in the ICU or intermediate care unit or hospital). The volume should be corrected to account for the volume of samples previously taken from the total urine initially collected.
  - p. Only when possible within the 24-hour time window from first AKI diagnosis to treatment.
  - q. Assays will be performed by a central reference laboratory. See Section 6.3.8.3 for sampling details.
  - r. A 12-lead ECG with at least 30-second rhythm strip will be recorded after the patient has rested supine or semi-recumbent for at least 5 minutes.
  - s. Central reference laboratory.
  - t. Samples taken on Days 60 and 90 will only be analyzed in case of a positive result on Day 28.
  - u. Verification that no concomitant medications that should be avoided are taken.

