Exploratory analysis of the total number of days on RRT will be undertaken for the comparison of the optimal recAP dose and placebo using an ANOVA with treatment and site as explanatory variables. The least square means for each treatment and the difference in least squares means between the treatment groups will also be presented along with the associated 95% CI and p-value. If a subject withdrew from study or died while still on RRT treatment before Day 28, then duration of RRT (ie, number of days on RRT) will be calculated as from RRT start date up to Day 28 (ie calculating with the "remaining days up to Day 28). For the calculation of total number of days on RRT, any missing RRT stop days will be set to either the day before the next RRT start date if more than one RRT record or to Day 28 if the patient has no further RRT records.

All RRT data will be listed.

Kidney function

The reference eGFR will be estimated by the CKD-EPI formula based on the reference serum creatinine value recorded on the AKI Diagnosis page of the eCRF for each patient. The reference serum creatinine value is recorded on the eCRF using the following order of preference:

1. Lowest value within 3 months of the hospital admission; if not available then:
2. Value at hospital admission; if not available then:
3. Value ICU/Intermediate care admission; if not available then:
4. Lowest value between 3 and 12 months prior to hospital admission

Baseline serum creatinine from the laboratory data will not be included in the calculation of reference eGFR.

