Kidney function will be assessed at Baseline, Day 14, 21 and 28 by measured creatinine clearance. Baseline kidney function will only be measured by standardized creatinine clearance, however for Day 14, 21 and 28 summaries if creatinine clearance is not available then kidney function as assessed by eGFR (estimated by the CKD-EPI formula based on serum creatinine) will be used.. Kidney function will also be assessed at Day 60 and Day 90 by eGFR. Sustained loss of Kidney function, defined by eGFR < 60 mL/min, will be assessed at Day 60 and Day 90. The analyses of kidney function and sustained loss of kidney function at each timepoint will exclude any patients who die prior to the timepoint. Any other missing assessments (including early withdrawals) at Day 60 or Day 90 will be imputed by LOCF where possible, missing Day 14, 21 and 28 values will not be imputed and will be treated as missing. A summary table will present descriptive statistics for the reference kidney function and the kidney function at Baseline and at Days 14, 21, 28, 60 and 90 along with counts and percentages of patients with loss of sustained kidney function at Day 60 and Day 90. Descriptive statistics will also be presented for the change from baseline creatinine clearance value at Day 14, Day 21, Day 28, Day 60, and Day 90.

The absolute difference between placebo and each of the treatment groups will also be presented at each time point. Summaries for Day 60 and 90 will be repeated with and without the LOCF imputation of missing values applied.

All kidney function data will be listed.

Dialysis Dependency

Incidence of dialysis dependency will be assessed at Day 60 and Day 90. Patients who die or withdraw from the study prior to Day 60 or Day 90, respectively, without recording incidence of chronic dialysis will be counted as not being dialysis dependent. A summary table will present the counts and percentages of patients who are dialysis dependent at Day 60 and Day 90. Percentages for each timepoint are calculated based on the number of patients that were assessed including those who died or withdrew prior to timepoint.

All data on dialysis dependency will be listed.

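### At Days 60 and 90 the SAP's change in kidney function subtracts a measured creatinine clearance from a CKD-EPI eGFR, so its size within an arm is not a change in kidney function

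*SAP*

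**What the plan says.** The kidney-function part of SAP 8.2.2.1 sets the measure visit by visit.

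- **Baseline:** "Baseline kidney function will only be measured by standardized creatinine clearance".
- **Days 14, 21 and 28:** measured clearance, but "if creatinine clearance is not available then kidney function as assessed by eGFR" is used instead.
- **Days 60 and 90:** "Kidney function will also be assessed at Day 60 and Day 90 by eGFR".
- **Change:** the summary table is to show the "change from baseline creatinine clearance value at Day 14, Day 21, Day 28, Day 60, and Day 90".
- **Missing values:** "Any other missing assessments (including early withdrawals) at Day 60 or Day 90 will be imputed by LOCF where possible". Missing Day 14 to 28 values stay missing. The Day 60 and 90 summaries are produced both with and without this imputation.

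The same table holds a pre-illness comparator on the eGFR scale: "The reference eGFR will be estimated by the CKD-EPI formula based on the reference serum creatinine value" recorded at AKI diagnosis. SAP 6.2 also summarizes baseline eGFR. No change from either is requested. SAP 8.2.2.1 also asks for the absolute difference between placebo and each treatment group at each time point, without saying whether this refers to the level or to the change.

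**The concern.** A change score is interpretable only if both ends measure the same thing. Here the two ends come from different formulas. Standardized clearance (SAP 8.1) depends on urine volume and urine creatinine, and is set to 0 when urine volume is 0. CKD-EPI (SAP 15.4) uses serum creatinine, age, sex and race, and no urine data. Protocol 13.5.1 itself warns that creatinine clearance can over- or under-estimate function in unstable states such as AKI, and AKI is every patient's baseline state.

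The protocol justifies the 90-day follow-up by its ability to show whether CKD develops or worsens. A row that appears to show recovery from baseline to Day 90, when part of the figure is a switch of method, could be quoted as evidence on that question.

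**Working it through.** The plan states no figure for this variable, so there is none to reproduce. The check traces the measure at each visit and then sizes the offset from the SAP's own formulas.

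**1. What can exist at each visit.** Protocol Table 13-1 states: "At Days 60 and 90, only serum creatinine will be measured". The footnotes to SAP Table 15-1 repeat this. No clearance can be calculated at Days 60 and 90, so an observed change there can only be eGFR minus baseline clearance. If the sentence is read as change in clearance alone, those two visits have no observed data, although the SAP lists them. The SAP change history for version 3.0 records the clearance-only baseline and the Day 14 to 28 fallback as intended.

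**2. Within an arm at Days 60 and 90.** Write CL for clearance, with subscript 0 for baseline and v for the visit.

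eGFR_v − CL_0 = (eGFR_v − eGFR_0) + (eGFR_0 − CL_0)

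The first bracket is the like-for-like change. The second is the method difference at baseline, and it enters every observed value.

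**3. Size in one patient.** Assumptions: man aged 60, not black, 80 kg, serum creatinine 2.0 mg/dL at both times.

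- eGFR = 141 × (2.0/0.9)^−1.209 × 0.993^60 = 35.2.
- Baseline urine volume 0: clearance is 0 by the SAP rule, so the reported change is +35.2 mL/min. On the same rule it is +49.9 at a serum creatinine of 1.5 mg/dL and +15.2 at 4.0.
- Baseline urine at the 0.5 mL/kg/h threshold: flow = 0.5 × 80 / 60 = 0.667 mL/min, and clearance = (urine creatinine / 2.0) × 0.667.

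| Urine creatinine (mg/dL) | Clearance (mL/min) | Reported change with no true change (mL/min) |
|---|---|---|
| 40 | 13.3 | +21.9 |
| 60 | 20.0 | +15.2 |
| 100 | 33.3 | +1.9 |

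The sign is not fixed. At serum creatinine 3.0 and urine creatinine 100, clearance is 22.2 and eGFR 21.6, so the artefact is −0.6.

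**4. Between arms at Days 60 and 90, observed values.** The difference in mean change is the difference in mean eGFR_v minus the difference in mean CL_0. Baseline clearance precedes treatment, so the second term is near zero in expectation. This is only approximate, because deaths before the visit and patients without a baseline clearance drop out.

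**5. Days 14 to 28.** Protocol 6.3.8.1 explains most of the missing clearances: "When patients are discharged from the hospital, 6-hour urine collection at home is not considered feasible or reliable". Patients who leave the ICU but remain in hospital are still to be collected from. For a patient on the fallback, the change gains the visit-time offset (eGFR_v − CL_v). If that offset has the same mean d in both arms, the between-arm artefact is d × (difference in the share of patients on eGFR). The documents give neither input. Assuming d of 10 to 30 mL/min and a share difference of 5 to 20 points gives 10 × 0.05 = 0.5 up to 30 × 0.20 = 6.0 mL/min; for example, 20 × 0.10 = 2.

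**6. LOCF.** The rule does not say that the carried value must be an eGFR. A Day 28 clearance could therefore enter the Day 60 or 90 summary and be judged against the eGFR < 60 mL/min threshold for sustained loss.

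**The case against.** A reader might infer that the Day 60 and 90 comparison between arms is also uninterpretable. For observed values the documents do not support that. All arms use the same pair of measures, and the baseline term roughly cancels (step 4).

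A reader might also infer that every Day 60 and 90 change mixes methods. That fails for a carried-forward clearance, where that patient's change is clearance minus clearance. The LOCF row is then mixed across patients instead. A version without LOCF is planned. Serum creatinine is scheduled at every visit, so an earlier eGFR can normally be derived, and carrying eGFR is the natural reading because the endpoint is defined as eGFR. What stands is that the SAP does not say so.

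Nor does the 90-day assessment of CKD rest on this row. The SAP also gives eGFR levels beside the reference eGFR, sustained loss, dialysis dependency, composites 2 and 3 (8.3), and change in serum creatinine to Day 90 (8.2.2.3), which is like for like. Protocol 7.3.1 defines the endpoint as a level, not a change.

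Two further points stand. The Day 28 fallback comes from the protocol, so its use for the level is not at issue here. And a baseline eGFR taken during AKI has its own weakness: protocol 13.5.1 notes that creatinine-based estimates are considered unreliable when renal function is not in steady state. None of this makes eGFR minus clearance a change in kidney function.

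**Conclusion.** The point holds within limits. At Days 60 and 90 every observed change subtracts a measured clearance from an eGFR, and its within-arm size is not interpretable. That follows from the text without any assumption. The +1.9 to +35.2 mL/min range is an illustration for one assumed patient at serum creatinine 2.0 mg/dL, not an estimate for the trial.

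At Days 14 to 28, distortion between arms is possible if the share of patients without a clearance differs by arm. Its size and direction cannot be computed from the documents; the 0.5 to 6.0 mL/min range rests wholly on assumed inputs. The LOCF point is a gap in wording that could affect the imputed summary and the sustained-loss classification.

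The table is descriptive, and the SAP treats analyses of the other secondary endpoints as exploratory. No test or decision depends on it, and the primary and key secondary analyses are unaffected.

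**What to change.** In SAP 8.2.2.1:

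1. At Days 60 and 90, report change in CKD-EPI eGFR from the reference eGFR already in this table. Change from baseline eGFR may be added, with a note that eGFR is unreliable in non-steady-state AKI.
2. At Days 14, 21 and 28, compute change from baseline clearance only where the visit value is also a measured clearance, and show the number of patients per measure in each arm.
3. State that LOCF to Days 60 and 90 carries eGFR values only, including for the eGFR < 60 mL/min classification.

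The cost is SAP wording and table shells. All inputs are already collected, and both the reference and the baseline eGFR are already derived. The protocol does not define the change variable, so this needs no protocol amendment.

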  - Sustained loss of kidney function at Day 60 and Day 90, defined by  $eGFR < 60$  mL/min (with eGFR estimated by the CKD-EPI formula based on serum creatinine). Patients who die prior to Day 60 or Day 90, respectively, will be excluded from this endpoint, with any other missing assessments (including early withdrawals) at Day 60 or Day 90 imputed using LOCF.
  - Incidence of dialysis dependency at Day 60 and Day 90. Patients who die or withdraw from the study prior to Day 60 or Day 90, respectively, without recording incidence of dialysis dependency will be counted as not having required dialysis dependency.

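### Patients who withdraw before Day 60 while on RRT are scored as not dialysis dependent, which can only lower the reported rate, and no alternative version is planned

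*SAP*

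**What the plan says.** **Dialysis dependency.** In SAP 8.2.2.1 (Dialysis Dependency), patients who die or withdraw before the visit "without recording incidence of chronic dialysis will be counted as not being dialysis dependent". The denominator is also set: "Percentages for each timepoint are calculated based on the number of patients that were assessed including those who died or withdrew prior to timepoint". Protocol 7.3.1 agrees in substance: such patients "without recording incidence of dialysis dependency will be counted as not having required dialysis dependency". The output is counts and percentages at Days 60 and 90, plus a listing.

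**When it is recorded.** Protocol 6.3.9 and the schedules (protocol Table 13-1, SAP Table 15-1) collect dependency only at Days 60 and 90. RRT use, with start and stop dates, is scheduled from Day 1 to Day 28.

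**Related endpoints in the SAP.**
- Days on RRT (8.2.2.1, RRT): "If a subject withdrew from study or died while still on RRT treatment before Day 28", the duration "will be calculated as from RRT start date up to Day 28".
- Kidney function and sustained loss (8.2.2.1, Kidney function): the analyses "will exclude any patients who die prior to the timepoint". For the rest, "Any other missing assessments (including early withdrawals) at Day 60 or Day 90 will be imputed by LOCF where possible". The Day 60 and 90 summaries are given with and without that imputation.
- RRT incidence, the key secondary endpoint (8.2.1): death or withdrawal without recorded RRT counts as no RRT, but the analysis is repeated without patients who died or withdrew.
- Composites 2 and 3 (8.3): both include a dialysis-dependency component. No missing-data rule is stated for them.

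**The concern.** The rule exempts patients for whom dialysis was already recorded. Because the item is collected only at Days 60 and 90, that exemption gives little protection to someone who leaves before Day 60. Such a patient is scored as a non-event even when the RRT dates show that they were on RRT at exit.

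The 90-day follow-up is there to look for lasting effects on the kidney, and this table reports dialysis need directly at those two visits. A rule that turns unknown status into the favourable answer makes the percentage a lower bound without labelling it as one. If leaving on RRT were more common in one arm, the table would flatter that arm, and no planned output for this endpoint would show how much the result depends on the assumption.

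**Working it through.** The plan states no expected rate, power or sample size for dialysis dependency, so there is no figure to reproduce. The check has three parts: direction, size per patient, and an illustration on assumed inputs.

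**Inputs from the documents.** Planned sample size (SAP 4.1): 4 × 30 + 2 × 85 = 290. The optimal-dose and placebo arms each have 30 + 85 = 115.

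**Assumed inputs, not in the documents.** k = patients per arm who withdraw on RRT before Day 60, taken as 3 to 10. q = the share of them truly dependent at the visit, taken as 25% to 100%.

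**Direction.** With the denominator fixed at all patients, a withdrawn patient of unknown status contributes 0. The true contribution is 0 or 1. The reported rate is therefore at or below the true rate.

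**Size per patient.** 1/115 = 0.87 percentage points.

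**Range.** Points lost = 100 × k × q / 115:

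| k | q = 25% | q = 50% | q = 100% |
|---|---|---|---|
| 3 | 0.65 | 1.30 | 2.61 |
| 5 | 1.09 | 2.17 | 4.35 |
| 10 | 2.17 | 4.35 | 8.70 |

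**Worked example, leaving deaths aside.** Assume 10 recorded dependants and 5 withdrawals on RRT in an arm of 115:
- SAP rule: 10/115 = 8.7%
- the 5 excluded as unknown: 10/110 = 9.1%
- the 5 carried forward as dependent: 15/115 = 13.0%

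The last two figures show how far the answer moves with the assumption. The plan would print only the first.

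**Deaths.** Reported rate = (1 − mortality) × rate among survivors. With an assumed 10% among survivors and mortality of 30%, 50% or 70% (the protocol introduction cites up to 70%), the table shows 7%, 5% or 3%. This is dilution by a different definition of the population, not misclassification, and is kept apart from the withdrawal point.

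**The case against.** A reader might infer that the SAP contradicts itself by placing the same patient on RRT to Day 28 and then off dialysis at Day 60. The documents do not support that. The Day 28 rule concerns days on RRT, a different endpoint and window, and a patient can be on RRT through Day 28 and independent by Day 60. What remains is an inconsistency of assumption: last status is extended for one endpoint and reset to the favourable value for the other.

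A reader might also infer that the rule overrides known dependency. It does not. RRT dates to Day 28 describe acute treatment, and status at Day 60 after withdrawal is unknown. For the same reason, carrying RRT status forward to Day 90 as the main analysis would replace a best case with a worst case. That objection stands, and carry-forward belongs only in a sensitivity analysis.

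The handling of deaths is partly a choice of estimand. Counting deaths as non-events over all patients matches the main RRT-incidence rule. Mortality is reported separately (SAP 8.2.2.2), and the composites count death. Suppose 10% of survivors are dependent in both arms and mortality is 20% against 35%. The dependency table shows 0.10 × 0.80 = 8.0% against 0.10 × 0.65 = 6.5%, but the death-or-dialysis parts of composite 2 show 28.0% against 41.5%. A reader of both outputs would not be misled about the arm with more deaths. Restricting to survivors has its own weakness, since survivors are a subset formed after randomisation.

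The follow-up provisions also reduce the problem. Protocol 4.2.1 and 4.2.2 ask that patients who stop drug preferably stay in follow-up and that withdrawn patients return for Day 90 if they agree. A patient recorded as dependent at Day 60 who leaves before Day 90 would arguably still count. The point therefore bites mainly on withdrawals before Day 60.

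Finally, the SAP follows the protocol here, the endpoint is exploratory with no test planned, and the RRT and dependency data are listed. All of this limits the consequence. None of it supplies the missing alternative version.

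**Conclusion.** The point holds as a one-directional understatement in an exploratory, descriptive endpoint. Withdrawals before Day 60 on RRT are scored as favourable, and no sensitivity version is planned, unlike for RRT incidence and Day 60/90 eGFR.

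The firm size is 0.87 points per misclassified patient at 115 per arm. The range of 0.65 to 8.70 points rests wholly on assumed values of k and q.

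It is tempting to conclude that the treatment comparison is biased. That would need withdrawal on RRT to differ between arms, and nothing in the documents shows that it will. It is also tempting to say that the composites miss withdrawals on RRT. SAP 8.3 gives no missing-data rule, and such a patient might still qualify through the eGFR component, so the most that can be said is that the handling is unspecified.

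**What to change.** In SAP 8.2.2.1, with matching wording in protocol 7.3.1:

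1. Stop counting withdrawals of unknown status as not dependent. Report the Day 60 and Day 90 percentages among patients alive with known status.
2. Beside them, show by arm the numbers who died and who withdrew, each split by on or off RRT at exit, using the RRT dates already in the eCRF.
3. Add a sensitivity version that carries forward last known RRT status for withdrawals. Label it an upper bound, on the assumption that nobody off RRT at exit became dependent later.
4. Keep the all-patient version as a secondary row, so that a comparison of everyone randomised remains available.
5. In SAP 8.3, state a missing-data rule for composites 2 and 3 and apply the same withdrawal sensitivity to their dialysis component.
6. Define chronic dialysis, which the SAP uses where the protocol refers to dialysis dependency.

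The cost is wording and some extra programming; no new data are needed. The headline percentage becomes less favourable. In the worked example it moves from 8.7% to 9.1% through withdrawals alone. Taking deaths out of the denominator raises it further (from 7% to 10% at an assumed 30% mortality), so the table should say that this part of the shift is a change of population.
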